8.4 Data Monitoring Committee

An external independent Data Monitoring Committee (DMC) will be appointed to monitor the safety of study participants and to ensure that the program is being conducted with highest scientific and ethical standards. This DMC will review the safety data throughout the trial. Should the DMC make recommendations on the conduct of the trial that are considered to have significant bearing on the benefit-risk of the trial, these will be communicated by DMC to Executive Committee members and Novartis. The final decisions will be communicated to the investigators within an appropriate timeframe.

8.5 Adjudication Committee

To strengthen the efficacy findings and interpretation, a Central Event Committee will be instituted and will oversee the adjudication of in-hospital WHF events and the cause of death.

A charter of responsibilities and a specific dataset to evaluate clinical cases will be available before study initiation (Endpoint Manual).

The adjudication committee will review and adjudicate all in-hospital WHF that occur through Day 5 for endpoint determination in a blind way, as well as the causes of death events. The detailed definitions of the endpoints, required documentation, and the adjudication process will be provided to all sites in a separate Endpoint Manual.

9 Data analysis

All the data collected in this study will be listed and summarized as appropriate as described below. The data from all countries and all centers will be pooled and summarized. Continuous data will be summarized by the mean, standard deviation (SD), median, first and third quartiles, minimum and maximum. Categorical data will be presented by absolute and relative frequencies (n and %) or contingency tables.

Subjects will be included in each efficacy analysis based on available assessments, after the data handling conventions have been applied. The prevalence approach, if not differently indicated, will be applied.

Unless stated otherwise, two-sided p values <0.05 will be considered statistically significant. All statistical tables, listings and analyses will be produced using SAS® release 9.2 or later (SAS Institute, Inc, Cary, NC, USA).

More details about data analysis will be provided in the Statistical Analysis Plan.

9.1 Analysis sets

The following analysis populations will be defined for statistical analysis.

Patients without a valid or adequately obtained Informed Consent Form (ICF) will be excluded from any analysis population.

9.1.1 Full analysis set (FAS)

The Full Analysis Set (FAS) will include randomized patients who were not mis-randomized.

Following the intent-to-treat (ITT) principle, patients are analyzed according to the treatment they have been assigned to at randomization. Mis-randomized patients are those who have not qualified for randomization, have been inadvertently randomized into the study but who did not enter the treatment phase and who did not receive serelaxin. Mis-randomized patients are defined as cases where randomizations were made by the site either prematurely or inappropriately prior to confirmation of the patient's final randomization eligibility. These patients should subsequently be discontinued from the study. The primary analysis and the analyses of all secondary and exploratory efficacy variables will be based on the FAS.

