5.3 Treatment assignment, randomization

At baseline, all eligible patients will be randomized via Interactive Response Technology (IRT) to one of the treatment arms. The investigator or his/her delegate will contact the IRT after confirming that the patient fulfills all the inclusion/exclusion criteria. The IRT will assign a randomization number to the patient, which will be used to link the patient to a treatment arm and will specify a unique medication number (for patients randomized to serelaxin only) for the first package of investigational treatment to be dispensed to the patient. The randomization number will not be communicated to the caller.

The randomization numbers will be generated using the following procedure to ensure that treatment assignment is unbiased. A patient randomization list will be produced by the IRT provider using a validated system that automates the random assignment of patient numbers to randomization numbers. These randomization numbers are linked to the different treatment arms, which in turn are linked to medication numbers (for serelaxin arm only). A separate medication list will be produced by or under the responsibility of Novartis Drug Supply Management using a validated system that automates the random assignment of medication numbers to packs containing the investigational drug.

The randomization scheme for patients will be reviewed and approved by the Randomization Office.

Mis-randomized patients are those who have not been qualified for randomization, have been inadvertently randomized into the study and who did not take study drug. Mis-randomized patients are defined as cases where IRT calls were made by the site either prematurely or inappropriately prior to confirmation of the patient's final randomization eligibility and administration of serelaxin, where applicable, was not performed. These patients should have been considered screen failures as they did not meet eligibility criteria and should subsequently be discontinued from the study. Sites should notify IRT and contact their Novartis monitor as soon as possible if a patient is mis-randomized into the study.

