5.4 Treatment blinding

Treatment code will be open to patients, investigator staff, and persons performing the assessments. The clinical trial team (e.g. Clinical Trial Lead, Clinical trial Manager, Medical Lead, Trial Statistician) will be blinded to the identity of the treatment from the time of randomization until database lock. Randomization data will be kept strictly confidential until the time of unblinding, and will not be accessible by anyone else involved in the study with the exception of those mentioned in the Safety Manual.

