5.5 Treating the patient

5.5.1 Patient numbering

Each patient is uniquely identified by a Subject Number which is composed by the site number assigned by Novartis and a sequential number assigned by the investigator. Once assigned to a patient, the Subject Number will not be reused.

Upon signing the informed consent form, the patient is assigned the next sequential number by the investigator. The investigator or his/her staff will contact the IRT and provide the requested identifying information for the patient to register them into the IRT. The assigned patient number should be entered in the field labeled “Subject ID” on the electronic Case Report Form (eCRF) data entry screen.

If a patient correctly randomized fails to be treated for any reason, the IRT must be notified immediately that the patient was not treated. The patient will be followed up to Day 30 and relevant information, together with the reason for not being treated, will be entered into the eCRF.

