5.5.5 Permitted dose adjustments and interruptions of study treatment

Systolic Blood Pressure (SBP) has to be ≥ 125 mmHg for the patient to be eligible, and then ≥ 125 mmHg during the screening period, in particular at the end of the screening period just before calling the IRT for randomization. In many centers, continuous cardiac monitoring will probably be applied and this will keep the site informed about SBP values.

Considering the high fluctuation of blood pressure in patients with decompensated HF, especially because the patient might be under the effect of nitrates (even at low dose) and diuretics, it is advised to minimize the time windows between the end of screening, the IRT call and start of the serelaxin infusion.

In practice:

- BP has to be measured at the end of screening and SBP must be ≥ 125 mmHg before calling the IRT. Once the patient is randomized, the study drug should be prepared promptly (if the patient is in the serelaxin group).
- Just before the immediate start of study drug infusion, SBP must be assessed again. During that interval between randomization and infusion start, sometime will elapse (30 to 60 minutes in most cases) and BP may fluctuate.
 - It is not required that pre-infusion SBP be ≥ 125 mmHg (SBP ≥ 125 mmHg is an inclusion criterion and matters only up to randomization)
 - If at the immediate start of study drug infusion, SBP is below 100 mmHg (SBP < 100 mmHg), serelaxin should not be started, neither now nor later. The patient will remain in the study up to 30 days but will not have received serelaxin
 - If a blood pressure fall has occurred since randomization but SBP is still ≥ 100 mmHg, the decision to start or not the infusion remains at the discretion of the investigator, based on the hemodynamic context of the patient (i.e. previous hemodynamic stability, DBP, concomitant medications, medical response to IV furosemide/diuretics, etc.).

Of note, there is no mandatory time window between randomization and start of the study drug infusion. This time span should be kept as short as possible. For microbiological reasons, there is a maximum time of 4 hours allowed between preparation (mixing) of the study drug and infusion start.

If at any time during the study drug infusion, the subject's systolic blood pressure decreases by >40 mm Hg from just before the study drug infusion but is ≥ 100 mmHg in two consecutive measurements 15 min apart, the serelaxin infusion rate will be decreased by 50% for the

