2.2. TREATMENT GROUPS AND RANDOMIZATION

Subjects are randomized in a 2:1 ratio to receive one of the following:

- Serelaxin (30 µg/kg/day) as continuous 48-hour intravenous infusion plus standard of care.
- Standard of care only.

At baseline, all eligible patients who fulfill all inclusion/exclusion criteria are randomized via Interactive Response Technology (IRT) to one of the treatment arms.

	Statistical Analysis Plan
	Sponsor: NOVARTIS Protocol number: CRLX030A3301

The IRT assigns a randomization number to the patient, which links the patient to a treatment arm, and specifies a unique medication number (for patients randomized to serelaxin only) for the first package of investigational treatment to be dispensed to the patient. The randomization number is not communicated to the caller.

The randomization numbers are generated using the following procedure to ensure an unbiased treatment assignment. A patient randomization list is produced by the IRT provider using a validated system that automates the random assignment of patient numbers to randomization numbers. These randomization numbers are linked to the different treatment arms, which in turn are linked to medication numbers (for serelaxin arm only). A separate medication list is produced by or under the responsibility of Novartis Drug Supply Management using a validated system that automates the random assignment of medication numbers to packs containing the investigational drug.

Mis-randomized patients are those who have not been qualified for randomization, have been inadvertently randomized into the study and who did not take study drug. Mis-randomized patients are defined as cases where IRT calls were made by the site either prematurely or inappropriately prior to confirmation of the patient's final randomization eligibility and administration of serelaxin, when applicable, was not performed. These patients should have been considered screen failures as they did not meet eligibility criteria and should subsequently be discontinued from the study. Sites should notify IRT and contact their Novartis monitor as soon as possible if a patient is mis-randomized into the study.

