	Subject not randomized but entered the treatment phase	PROC06		X	X	X	
	Subject mis-randomized (i.e. subject who has not been qualified for randomization, has been inadvertently randomized into the study, who did not enter the treatment phase and who did not undergo Serelaxin administration)	PROC07			X	X	X

* Deviations codes as defined in the Protocol Deviation Handling Document (blind & unblind). Codes could possibly change before database lock.

In addition, deviations not defined in the protocol resulting in exclusion of subjects from an analysis population are outlined in the table below.

Table 3-2: Non-protocol deviations resulting in exclusion of subjects from analysis populations

Category	Description	Non-Protocol Deviation	Exclusion from analysis set				
			SCR	RAN	FAS	PP	SAF
Non-protocol deviation	Subject has no post-baseline safety assessment.						X

	Statistical Analysis Plan
	Sponsor: NOVARTIS Protocol number: CRLX030A3301

Category	Description	Exclusion from analysis set				
		SCR	RAN	FAS	PP	SAF
Non-protocol deviation	Subject randomized to Serelaxin group but not receiving any dose of study medication				X	X

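### Mis-randomization, which removes patients from the FAS, is defined inconsistently and rests on post-randomization conditions that work differently in the two arms, and no planned analysis would show the effect on the primary result

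*Protocol*

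**What the plan says.** Protocol 9.1.1 and SAP 3 form the FAS from randomized patients who were not mis-randomized, analysed by assigned arm under the intent-to-treat principle. For a randomized patient the only other ground for removal is invalid consent. As far as the broken columns of SAP Table 3-1 can be read, the other rows that touch the FAS concern patients who were never randomized.

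Mis-randomization is worded in three ways:

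- **Wording A** (Protocol 5.3, SAP 2.2). The patient did not qualify, was randomized in error and took no study drug. The next sentence adds that "administration of serelaxin, where applicable, was not performed" (SAP: "administration of serelaxin, when applicable, was not performed").
- **Wording B** (Protocol 9.1.1 and SAP 3, first sentence). The patient is one who has "not qualified for randomization, have been inadvertently randomized into the study but who did not enter the treatment phase and who did not receive serelaxin". SAP Table 3-1, code PROC07, agrees: "who did not enter the treatment phase and who did not undergo Serelaxin administration".
- **Wording C** (Protocol 9.1.1 and SAP 3, next sentence). The site randomized prematurely or inappropriately, before eligibility was confirmed. No dosing condition appears.

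On follow-up, Protocol 5.3 says: "These patients should have been considered screen failures as they did not meet eligibility criteria and should subsequently be discontinued from the study". A correctly randomized patient who goes untreated is handled differently in Protocol 5.5.1: "The patient will be followed up to Day 30 and relevant information, together with the reason for not being treated" are to be recorded.

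The primary, secondary and exploratory efficacy analyses use the FAS, and the supportive per-protocol (PP) set lies inside it (Protocol 9.1.3, SAP 5.2). The randomized set (RAN) is defined, but its only stated use is as denominator for population counts (SAP 5.1).

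**The concern.** Ineligibility and a premature IRT call are facts fixed before randomization, and excluding on them need not favour either arm. Entering the treatment phase and receiving serelaxin come afterwards, in a trial where, by Protocol 5.4, "Treatment code will be open to patients, investigator staff, and persons performing the assessments".

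In the serelaxin arm, removal depends on whether the error is noticed before infusion. Protocol 5.5.5 describes that window: "During that interval between randomization and infusion start, sometime will elapse (30 to 60 minutes in most cases) and BP may fluctuate". In the SOC arm there is no infusion to close the window. Every SOC patient who follows the assignment receives no serelaxin, and neither document says when the treatment phase begins for SOC.

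A set described as intent-to-treat could therefore lose patients at different rates by arm. Readers would see the removals but not what they did to the primary comparison. The label also decides whether an outcome is collected, because mis-randomized patients are discontinued.

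**Working it through.** **Step 1: the wordings side by side.** Take an ineligible patient randomized prematurely and ask whether that patient leaves the FAS.

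| Reading | Serelaxin, infused | Serelaxin, not infused | SOC |
|---|---|---|---|
| A, study drug meaning serelaxin | stays | removed | all removed |
| A, study drug including background therapy (Protocol glossary) | stays | stays if background therapy given | stays if background therapy given |
| B, SOC treatment starting at randomization | stays | removed | none removed |
| B, SOC entering the treatment phase at some later, undefined point | stays | removed | some removed |
| C alone | removed | removed | all removed |

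Row 3 borrows the SOC start time that Protocol 9.5.2 sets for adverse events and SAP 5.1 sets for baseline. Row 4 relies on SAP 5.1, which names a randomized treatment period without defining it for SOC. The serelaxin columns are stable across A (in its narrow sense) and B; the SOC column is not.

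**Step 2: possible size.** No planned figure is in dispute. The sample-size inputs are redacted, so 3183 cannot be rebuilt; it serves only to set arm sizes at 2:1, namely 3183/3 = 1061 SOC and 2122 serelaxin.

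Assumptions, none of them from the documents:

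- true null, with an 8% event rate in eligible patients (re);
- a share i of each arm, 1% or 3%, prematurely randomized and ineligible;
- an event rate ri of 2% or 16% in those patients;
- a quarter of them never infused, and so removed, in the serelaxin arm;
- 0, 25, 50 or 100% of them removed in the SOC arm.

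The event rate in an arm after removing a fraction x is f(x) = [(1−i)·re + (i−x)·ri]/(1−x). The risk ratio is f(xS)/f(xC), with xS = 0.25·i and xC = share·i.

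Worked example, i = 3%, ri = 2%, all such SOC patients removed:

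- f(0.0075) = (0.0776 + 0.00045)/0.9925 = 0.07864
- f(0.03) = 0.0776/0.97 = 0.0800
- risk ratio = 0.983

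One-sided error comes from simulating the Gehan test at nominal 0.025, with 40,000 trials per case (Monte Carlo SE 0.0008). With no exclusion it is 0.0270 (80,000 trials, SE 0.0006). Each cell below gives ri = 2% / 16%.

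| i | SOC share removed | Risk ratio | One-sided error |
|---|---|---|---|
| 1% | 0 | 1.002 / 0.998 | 0.0243 / 0.0248 |
| 1% | 25% | 1.000 / 1.000 | 0.0263 / 0.0279 |
| 1% | 50% | 0.998 / 1.002 | 0.0268 / 0.0246 |
| 1% | 100% | 0.994 / 1.008 | 0.0288 / 0.0227 |
| 3% | 0 | 1.006 / 0.993 | 0.0234 / 0.0291 |
| 3% | 25% | 1.000 / 1.000 | 0.0258 / 0.0275 |
| 3% | 50% | 0.994 / 1.007 | 0.0288 / 0.0237 |
| 3% | 100% | 0.983 / 1.023 | 0.0351 / 0.0170 |

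At 1%, about 5 serelaxin patients and 0, 3, 5 or 11 SOC patients leave. The error rates there are close to simulation noise: with no SOC removal and ri = 16%, the ratio leans towards serelaxin while the error falls. Only the last row shows a clear shift.

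**Step 3: a cruder cross-check.** Remove patients from SOC only and use a two-proportion normal approximation with a 6.5% rate in both arms (the serelaxin rate quoted in Protocol 1.1 for the earlier phase III trial). Removing 2% of SOC (21 patients) gives a one-sided error of 0.034, 0.029, 0.025 or 0.018 if those patients' event rate is zero, half, equal to or twice the average. The direction depends wholly on who is removed, and there is no effect if their rate is average.

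**Step 4: would RAN show it?** In the last row of the Step 2 table, a RAN analysis gives 0.0354 / 0.0171 if removed patients are censored at 1 minute, as SAP 5.2 requires when nothing is known after baseline. It gives 0.0262 / 0.0270 if they are followed.

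**The case against.** The strongest reply is that the analysis rule itself is consistent: Protocol 9.1.1, SAP 3 and PROC07 share wording B, while Protocol 5.3 is a site instruction and SAP 2.2 is background. Where a start time for SOC treatment is given, it is randomization. On that basis no SOC patient is removed, and the risk ratio stays between 0.993 and 1.006 even with 3% ineligible. This is a sensible reading, but the documents do not adopt it for mis-randomization. Wording C sits directly beside wording B, and the dependence on infusion in the serelaxin arm remains.

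A reader might infer that Protocol 5.3 and SAP 2.2 let every ineligible SOC patient be dropped. That is only one reading. Both also require that no study drug was taken, and the Protocol glossary counts background therapy as study drug, while Protocol 5.1.2 requires background therapy for all randomized patients. Elsewhere the documents use the term for serelaxin alone, so the clause blurs the rule rather than settling it.

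A reader might also infer that all ineligible patients leave the FAS, or that an imbalance would be hidden. Neither follows:

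- Eligibility deviations other than consent carry a single exclusion mark in Table 3-1, consistent with PP only. The removable group is confined to premature or inappropriate randomizations.
- Reasons for exclusion, the number mis-randomized and arm differences in deviations are all to be reported (Protocol 9.2, SAP 5.1).
- Eligibility is fully source-verified (Protocol 8.1), the trial team is blinded until lock (Protocol 5.4), and set allocation is approved before lock (SAP 3).
- The Protocol Deviation Handling Document, not available here, may contain an operating rule.

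These safeguards limit the problem. They do not reconcile the wordings, and the sites that make the erroneous randomizations know the arm.

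**Conclusion.** The point holds as a drafting and transparency defect in the primary analysis set. The definition of mis-randomization is inconsistent between sections and within Protocol 9.1.1 and SAP 3. It uses post-randomization conditions with no settled counterpart in SOC, and no efficacy analysis looks beyond the FAS.

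The size is unknown and probably negligible. Among the simulated cases a clear shift needs 3% of each arm ineligible, every such SOC patient dropped, and an event rate far from average; it then goes either way (risk ratio 0.983 or 1.023). The ineligible shares, their event rates and the 8% base rate are assumptions. There is no bias if removal is alike in both arms or unrelated to outcome.

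It would be wrong to conclude that the primary result is biased, or biased towards serelaxin. The documents give no mis-randomization count and no direction.

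**What to change.** Reconcile Protocol 5.3 and 9.1.1 with SAP 2.2 and 3 into one arm-neutral rule that removes no patient from the FAS on a post-randomization condition. The simplest version keeps every validly consented randomized patient in the FAS by assigned arm.

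If a mis-randomization exclusion is kept:

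- rest it only on eligibility facts documented before randomization, judged blind to arm;
- do not extend it to dosed patients. Under the Step 2 assumptions that would remove about 21 serelaxin patients instead of 5 at 1% ineligible, and 64 instead of 16 at 3%, moving further from intent-to-treat;
- report mis-randomized counts by arm;
- add a prespecified sensitivity analysis of the primary endpoint on RAN (valid consent), by assigned arm.

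In either case, follow mis-randomized patients still to be enrolled for WHF or death to Day 5 and for vital status to Day 30. Without follow-up RAN adds little, as Step 4 shows. At Amendment 4, 2337 patients had been randomized, so this could help only among the remaining 3183 − 2337 = 846 (27%).

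The cost is slight dilution from a few ineligible patients, one extra table if the exclusion stays, and a short amendment.

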9.1.2 Randomized (RAN) set

All patients who received a randomization number, regardless of receiving trial medication and including mis-randomized patients.

